***Electrical stimulation of the brain is seldom used to treat post-amputation pain***

In some cases, motor cortex stimulation (MCS) and deep brain stimulation (DBS) have reduced post-amputation pain by at least 50%, but the data is limited to small numbers of patients [REDACTED]. Despite the promising preliminary results, the authors and proponents of these studies caution that it is very difficult to predict which patients will benefit from treatment and that further study is still needed to test the effectiveness under double-blind conditions [REDACTED]. Due to cost and invasiveness, it is unlikely that either MCS or DBS will be recommended for post-amputation pain until additional clinical trials are performed to refine the patient selection criteria and confirm the long term effectiveness [REDACTED].

[REDACTED]

|            |            |            |            |
|------------|------------|------------|------------|
| [REDACTED] | [REDACTED] | [REDACTED] | [REDACTED] |
| [REDACTED] | [REDACTED] | [REDACTED] | [REDACTED] |
| [REDACTED] | [REDACTED] | [REDACTED] | [REDACTED] |
| [REDACTED] | [REDACTED] | [REDACTED] | [REDACTED] |
| [REDACTED] | [REDACTED] | [REDACTED] | [REDACTED] |

***Electroconvulsive therapy is rarely used to treat post-amputation pain***

There have been very limited reports on the use of electroconvulsive therapy (ECT) in the treatment of post-amputation pain. Small studies have described some benefit in amputee patients after all other options have been exhausted, but ECT is typically not recommended for amputee patients with post-amputation pain [REDACTED].

***High (> 1 kHz) frequency nerve block is not FDA-approved for pain relief in amputees and it is difficult to implement and maintain clinically***

Under controlled (laboratory) conditions, high frequency (e.g. > 1kHz) nerve block has been shown to decrease transmission of peripheral nerve signals, and case studies suggest it may reduce post-amputation pain, but it would require an invasive surgery to implant the electrodes around the nerve and it may be difficult to maintain sufficient nerve block in practice in ambulatory patients chronically in their home environment [REDACTED]. Additionally, blocking afferent signals from the peripheral source (e.g. neuroma) may decrease pain, but does not mediate the central mechanisms that develop during central sensitization in the chronic state. Thus, short-term nerve block is unlikely to be more effective in relieving post-amputation pain long-term than direct application of anesthetic to the peripheral nerve, which has been shown to be ineffective and is seldom used in relieving persistent post-amputation pain [REDACTED].

**3.2.2 Post-amputation pain may be reduced with peripheral nerve stimulation (PNS)**

***Peripheral nerve stimulation (PNS) can provide dramatic pain relief but the existing methods of implanting the lead are time consuming and complex, limiting widespread use***

[REDACTED] Peripheral nerve stimulation (PNS) has been shown to provide dramatic pain relief, improve sleep, increase quality of life, allow [REDACTED] patients to return to work, and reduce or eliminate dependence on opioid analgesia [REDACTED].

PNS is regarded as very effective in treating many types of neuropathic pain, including post-amputation pain [REDACTED].

[REDACTED]

Though PNS has a high success [REDACTED] the traditional method of surgically placing the lead is time consuming and complex because it requires careful open dissection of surrounding tissue to identify and prepare the target nerve for implantation of the electrode. At present, the extended time and complexity of the existing methods of surgical placement of the lead greatly limits the use of PNS outside of academic institutions [REDACTED].

[REDACTED]

### 3.2.3 Summary of feasibility study

*The previous feasibility study demonstrated that the proposed method of PNS can provide substantial relief of post-amputation pain*

[REDACTED]

*Data collected during the case-series home trial demonstrated pain relief and improvements in quality of life could be sustained*

[REDACTED]

[REDACTED]

[REDACTED]

[REDACTED]

[REDACTED]

*In addition to reductions in pain, significant improvements in quality of life were reported*

[REDACTED]

[REDACTED]

[REDACTED]

[REDACTED]

[REDACTED]

[REDACTED]

[REDACTED] *confirms the individual has the potential to receive pain relief from stimulation*

[REDACTED]

*Subjects* [REDACTED] *which can be an additional source of post-amputation pain*

[REDACTED]

Neuromas develop when a peripheral nerve is cut and the proximal portion produces new axon growth that forms a tangled mass as it fails to connect with the missing distal portion of the nerve. All amputations produce neuromas and not all neuromas are painful, but neuromas are thought to be a substantial source of pain after amputation [REDACTED]. Neuromas may generate spontaneous activity [REDACTED], and the level of activity in afferent fibers innervating the region of pain has been linked to the level of post-amputation pain [REDACTED]. In rats and rabbits, spontaneous and evoked activity has been recorded from neuromas, and the rate of activity increases when pressure is applied to the neuroma [REDACTED]. Injection of gallamine, which increases neuroma activity, increases pain, and injection of lidocaine, which decreases neuroma activity, decreases pain in amputees [REDACTED].

[REDACTED]

[REDACTED]

[REDACTED]

### 3.3 Summary

Present treatments for post-amputation pain are inadequate for many amputee patients and are associated with a lack of efficacy. [REDACTED]

[REDACTED]

The [REDACTED] study will use the proposed randomized placebo-controlled trial design to determine if the proposed method of percutaneous PNS can provide pain relief in Group #1 (Treatment) that is significantly greater than the placebo effect observed in Group #2 (Control). [REDACTED]

## 4.0 STUDY ENDPOINTS

### 4.1 Overview

Outcome measures will be administered to each subject at Baseline and at specified follow-up visits as described in Appendix A. To support the study endpoints, the following outcome measures will be used:

1. Diary

- Post-amputation pain [REDACTED]
  - Prosthetic usage
  - Medication affecting pain
2. Brief Pain Inventory, Short Form (BPI-SF)
  3. Pain Disability Index (PDI)
  4. Beck Depression Inventory, Second Edition (BDI-II)
  5. Patient Global Impression of Change (PGIC)
  6. Pain Catastrophizing Scale (PCS)

#### 4.2 The primary efficacy endpoint will be average pain intensity

The primary efficacy endpoint will be average post-amputation pain at the end of the [REDACTED] [REDACTED] trial (in both Treatment and Control groups) compared to baseline in all qualifying regions of post-amputation pain [REDACTED]. All amputees will record post-amputation pain scores [REDACTED] for [REDACTED] amputated leg [REDACTED].

[REDACTED] Each post-amputation pain region with [REDACTED] that receives an investigational device(s) will qualify to be used in the primary outcome analysis for that subject. [REDACTED]

The primary endpoint of the study compares the proportion of successes of Group #1 (Treatment) relative to that of Group #2 (Control), [REDACTED]

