| Additional Exclusion Criteria (verified after initial criteria verification) | 
 
• INR > 1.5 for those on warfarin
 
• Pregnant [REDACTED]
 
   |
| Primary Safety Endpoint  | 
 
• Occurrence of device-related and procedure-related adverse event rates. Adverse events will be assessed at all visits.
 
  |
| Primary Clinical Endpoint  | 
Pain Intensity: [REDACTED] post-amputation pain [REDACTED] that have intensities [REDACTED] during the baseline period and receive treatment with an investigational device will be used to assess the primary efficacy endpoint. All amputees will record [REDACTED] daily post-amputation pain scores [REDACTED] diaries using [REDACTED]. For each individual, [REDACTED] post-amputation pain [REDACTED] during baseline in a leg that receives blinded treatment from an investigational device(s) will qualify to be used in the determination of clinically-meaningful success for that subject throughout the study. Each amputee must have [REDACTED] reduction [REDACTED] to be considered a success in the primary effectiveness endpoint analysis.
 
The primary endpoint of the study compares the proportion of subjects in Group #1 relative to that in Group #2 that achieve [REDACTED] reduction in [REDACTED] post-amputation pain from baseline to the end [REDACTED] of the home trial, examining the statistical superiority of proportion of clinical successes of Group #1 over the proportion of successes of Group #2. The post-amputation pain intensity scores will be determined for each subject by taking the mean of the daily average pain intensity [REDACTED] reported in the [REDACTED] diary at baseline compared to the mean score for the same region(s) of pain reported [REDACTED].
 |
| Secondary Endpoints  | 
[REDACTED] Durability of the treatment effect for average pain intensity [REDACTED]
 
[REDACTED] Durability of the treatment effect for average pain intensity [REDACTED]
 
The following secondary outcomes will be measured [REDACTED]
 
 
• Pain interference [REDACTED]
 
• Pain disability (Pain Disability Index)
 
• Depression (BDI-II)
 
• Analgesic usage
 
• Prosthetic usage [REDACTED]
 
• Subject Satisfaction Survey
 
   |

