Pain relief will be evaluated using the average pain intensity. All regions of post-amputation pain (RLP or PLP or both) that have intensities  $\geq 4$  on average during the baseline period and receive treatment with an investigational device will be used to assess the primary efficacy endpoint. All amputees will record two daily post-amputation pain scores (one daily score for RLP and one daily score for PLP) for each amputated leg in the 7-day diaries using BPI-SF Question #5. For each individual, the region(s) of post-amputation pain with a 7-day average  $\geq 4$  during baseline in a leg that receives blinded treatment from an investigational device(s) will qualify to be used in the determination of clinically-meaningful success for that subject throughout the study. Each amputee must have  $\geq 50\%$  reduction in all areas of qualifying RLP and PLP to be considered a success in the primary effectiveness endpoint analysis.

The primary endpoint of the study compares the proportion of subjects in Group #1 relative to that in Group #2 that achieve  $\geq 50\%$  reduction in all areas of qualifying post-amputation pain from baseline to the first 4 weeks of the home trial, examining the statistical superiority of proportion of clinical successes of Group #1 over the proportion of successes of Group #2. The post-amputation pain intensity scores will be determined for each subject by taking the mean of the daily average pain intensity (BPI-SF Question #5) reported in the 7-day diary at baseline compared to the mean score for the same region(s) of pain reported over the first 4 weeks of the home trial (*i.e.*, the average of all diary scores during this period). For each leg with leads, the average pain scores will only include the days when all leads are in place (e.g., if leads are placed in second leg during week 2 of home trial, then only the data from weeks 2-4 will be used). Data will be collected as described in the Schedule of Procedures (Appendix A).

**9.1.1 Baseline characteristics and changes in usage of medication affecting pain will be analyzed to determine how strong their relationships are with changes in pain intensity between baseline and EOT**

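### Section 9.1.1 runs its covariate analysis to the end of treatment at week 8, although the primary outcome is a weeks 1-4 mean; the timing wording in 4.2 should also be aligned with 9.1

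*Combined protocol and SAP*

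**What the plan says.** **Primary outcome.** Section 9.1 is explicit. Each qualifying region's 7-day baseline diary mean is "compared to the mean score for the same region(s) of pain reported over the first 4 weeks of the home trial", and the text spells this out as "the average of all diary scores during this period". A subject succeeds with a reduction of at least 50% in every qualifying region. Three other places use the same window: the decision rule in 9.1, the imputation rule in 9.1.5, and the per-protocol definition in 9.5, which names the first 4 weeks as the primary endpoint period.

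**Covariate analysis.** The heading of 9.1.1 sets out to relate baseline characteristics and medication changes "with changes in pain intensity between baseline and EOT". The text beneath it lists the covariates, includes percent change in pain-medication use from baseline to EOT, and says the aim is to judge influence on the primary outcome.

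**Timing of EOT and crossover.** Section 7.5.11 places EOT at Visit 11, about 8 weeks after lead placement. Section 9.4 states that Group #2 receives stimulation in weeks 5-8.

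**Other wording of the endpoint.** Section 4.2 reads "The primary efficacy endpoint will be average post-amputation pain at the end of the", with the name of the period redacted. The synopsis reads "post-amputation pain from baseline to the end [REDACTED] of the home trial" where the matching sentence in 9.1 reads "from baseline to the first 4 weeks of the home trial". The synopsis sentence that would give the days averaged is redacted at exactly that point.

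**The concern.** A covariate analysis of the primary outcome should use the window in which that outcome is measured. As written, 9.1.1 does not. Its heading names a pain change that ends at week 8, its text names the primary outcome (weeks 1-4), and its medication covariate ends at week 8. After week 4 Group #2 is no longer on sham. A medication change measured to EOT therefore mixes the response to sham with the response to active stimulation in that group, and part of it comes after the outcome it is meant to explain. An apparent link with primary success, or the lack of one, could not be read as bearing on the 4-week sham comparison.

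The wording in 4.2 is a smaller matter. If relief builds or fades over the four weeks, a last-week score and a 4-week mean can put the same subject on opposite sides of the 50% line. The section that names the primary endpoint should not leave room for the wrong reading.

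**Working it through.** The plan gives no figure to reproduce on this point, and the assumed success rates behind the sample size are not visible. The first check sets the windows side by side. The second is illustrative arithmetic.

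**1. Windows in 9.1.1 against 9.1**

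| Quantity | Window | Group #2 treatment |
|---|---|---|
| Primary outcome (9.1, 9.1.5, 9.5) | weeks 1-4 | sham |
| Pain change in 9.1.1 heading | baseline to EOT (week 8) | sham, then active |
| Medication change in 9.1.1 text | baseline to EOT (week 8) | sham, then active |

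Section 9.1.1 does not say how medication use at EOT is computed. If it is averaged over the home trial, 4 of 8 weeks (50%) lie after the outcome window. If it is the last diary week, as 9.3 does for opioid use at week 8, the whole on-study measurement lies after the outcome window and after the crossover.

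**2. What a week-4 reading of 4.2 would change**

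Reduction = 1 - (on-study mean / baseline mean); success if at least 50%. Take baseline 6 and four weekly means:

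| Weekly means | 4-week mean reduction | Week-4 reduction |
|---|---|---|
| 5, 4, 3, 2 | 1 - 3.5/6 = 41.7% (fail) | 1 - 2/6 = 66.7% (success) |
| 3, 3, 3, 3 | 1 - 3/6 = 50% (success) | 50% (success) |
| 1, 2, 3, 4 | 1 - 2.5/6 = 58.3% (success) | 1 - 4/6 = 33.3% (fail) |

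For a linear ramp to a final reduction R, the 4-week mean is R x (0.25 + 0.50 + 0.75 + 1.00)/4 = 0.625R. Success on the mean then needs R of at least 0.50/0.625 = 80%, so any R from 50% to just under 80% succeeds at week 4 and fails on the mean.

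**3. How often, under assumed distributions**

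None of these inputs is in the documents: baseline mean 6, SD 1.2, floor 4; daily SD 1; full-effect reduction averaging 50% in Group #1 and 20% in Group #2, SD 30 points; one region; no missing days; the same time profile in both groups. There were 200,000 simulated subjects per arm and profile. Power is for 27 per group (Section 6.2), two-sided 5%, normal approximation for two proportions without continuity correction.

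| Share of full effect, weeks 1-4 | Group #1 classified differently | Group #1 success: 4-week mean / week 4 | Power: 4-week mean / week 4 |
|---|---|---|---|
| Immediate, stable (100% throughout) | 5.9% | 49.9% / 49.9% | 76.3% / 75.1% |
| Mild ramp (70, 90, 100, 100%) | 8.5% | 42.7% / 50.0% | 72.6% / 75.5% |
| Linear ramp (25, 50, 75, 100%) | 33.7% | 16.2% / 49.9% | 40.2% / 75.4% |
| Waning (100, 90, 80, 70%) | 14.1% | 38.5% / 25.0% | 69.0% / 52.7% |

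With an immediate, stable effect the disagreement is day-to-day noise and cancels in the success rate. A ramp favours the week-4 score; waning favours the 4-week mean.

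**The case against.** A reader might infer that the plan holds two or three competing primary endpoints, with the choice left open until the data are seen. The documents do not support that.

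- Section 9 gives one complete definition and keeps to it in the decision rule, the scoring text, the imputation rule and the per-protocol definition. An analyst following it has a single window.
- No visible sentence in 4.2 or the synopsis scores the last week alone. The synopsis averaging window is redacted and may be identical to 9.1. Parts of 4.2 are redacted as well.
- For the 8-week durability endpoint, 9.3 speaks of the end of the home trial and then scores the mean over all 8 weeks, stating that this is the primary endpoint's method. The phrase in 4.2 may be the same shorthand.
- The heading of 9.1.1 belongs to a covariate analysis and does not define an endpoint.

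All of this stands. Two things remain. The plan also uses end-of-period wording for a last-week score: opioid use at the end of the first 4 weeks comes from the week-4 diary only (9.3), so a reader of 4.2 alone cannot tell which sense applies. And the objection does not remove the mismatch in 9.1.1, which is unredacted: it carries the medication covariate to week 8 for an outcome that closes at week 4.

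**Conclusion.** The 9.1.1 window is wrong as written. It rests on unredacted text and needs no assumption about response: the covariate analysis extends 4 weeks beyond the primary outcome, into a period when both groups receive active stimulation. It affects the interpretation of a supporting analysis; the primary test as defined in 9.1 is untouched.

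The wording of 4.2 is a lesser inconsistency with 9.1. Whether the synopsis shares it cannot be checked. The consequence is conditional on someone reading 4.2 as week 4 only, and its size depends on the assumed time course: about 6% of Group #1 reclassified with no shift in success rate for an immediate, stable effect, and about 34% for a linear ramp. The direction reverses if relief wanes. These figures show what is possible and do not predict this trial.

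**What to change.** - In 9.1.1, change both the pain change in the heading and the medication change in the text so that they run from baseline to weeks 1-4, scored over the same days as the primary outcome. Medication change will still be measured after randomisation, so its association with success should be reported as descriptive.
- In 4.2, state the 9.1 definition (mean of all diary scores over weeks 1-4) as the only primary endpoint. Check the unredacted synopsis and align it if it differs.
- If a week-4 value is of interest, list it as a secondary or sensitivity analysis.

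The cost is protocol wording only. Visits, sample size and randomisation do not change, and the diary already records pain and pain-medication use.

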#### 4.3 Safety endpoint

The primary safety endpoint is the occurrence and type of device related adverse events (AEs). All AEs that occur during the study will be documented and analyzed. Specific details regarding any observed AE will be collected on an AE Form and will be followed to resolution. The investigator will determine the severity of each AE as well as its relationship to the device and procedure. In addition, each AE will be categorized as either serious or non-serious. Any necessary treatment or intervention required and the resolution status of the adverse event will also be documented. AEs will be tabulated and summarized at the conclusion of study. [REDACTED]

Additional details on the monitoring and adjudication of AEs is described in the section regarding monitoring.

#### 4.4 Secondary Efficacy Endpoints

Several secondary endpoints are being collected to gain a better understanding of what effect, if any, the interventions will have on each measure. We intend to evaluate these endpoints

(described below) to [REDACTED]. Refer to Section 9.3 for a detailed description of each endpoint. Changes from baseline will be evaluated as secondary efficacy endpoints for the following outcome measures:

- Durability of the treatment effect on average pain intensity [REDACTED]
- Durability of the treatment effect on average pain intensity [REDACTED]
- Pain interference (BPI-SF Question #9) [REDACTED]
- Pain disability (Pain Disability Index (PDI)) [REDACTED]
- Depression (Beck Depression Inventory (BDI-II)) [REDACTED]
- Analgesic usage [REDACTED]
- Prosthetic usage [REDACTED]
- Subject Satisfaction Survey

#### 4.5 Exploratory Analyses

Additional analysis will be conducted including:

- Treatment effect in Group #2 [REDACTED]
- Global impression of change (Patient Global Impression of Change (PGIC)) [REDACTED]
- Analyses of changes in average RLP [REDACTED]
- Analyses of changes in average PLP [REDACTED]
- Analyses of changes in worst RLP [REDACTED]
- Analyses of changes in worst PLP [REDACTED]
- Non-opioid medication use [REDACTED]
- Pain Catastrophizing Scale (PCS) [REDACTED]
- Clinician Satisfaction Survey

#### 5.0 Investigational Device Description

##### 5.1 Overview

This study utilizes the SPRINT PNS System. [REDACTED]

5.2

[REDACTED]

[REDACTED]

[REDACTED]

[REDACTED]

[REDACTED]

[REDACTED]

[REDACTED]

[REDACTED]

[REDACTED]

[REDACTED]

[REDACTED]

[REDACTED]

[REDACTED]

[REDACTED]

[REDACTED]

[REDACTED]

[REDACTED]

[REDACTED]

[REDACTED]

[REDACTED]

[REDACTED]

[REDACTED]

[REDACTED]

**6.0 Scope**

**6.1 Number of sites**

Multi-center Study [REDACTED]

**6.2 Number of subjects**

[REDACTED]

Up to 54 individuals will be enrolled as subjects and randomized to either Group #1 or Group #2 using a 1:1 randomization scheme. A total of up to 54 subjects (27 subjects per group) will undergo lead placement. [REDACTED]

### 6.3 Study duration

The duration of this study is expected to be approximately 2 years. [REDACTED]

## 7.0 Study protocol

### 7.1 Overview

This study is a randomized, double-blinded, placebo-controlled, multicenter pilot study to evaluate the safety and effectiveness of the SPRINT peripheral nerve stimulation (PNS) system for the treatment of post-amputation pain.

### 7.2 Study population

Subjects with post-amputation pain will be recruited by the investigators, following all HIPAA guidelines, to ascertain their level of interest and willingness to take part in this project. Recruitment materials will be provided to aid in subject enrollment. [REDACTED]

[REDACTED] All recruitment materials will be IRB approved prior to their use.

### 7.3 Concurrent medications and non-drug therapies

All interventions targeting pain control will be recorded in the Case Report Form (CRF) and patient diaries.

#### ***Daily medications affecting pain will be permitted at levels established during baseline***

All subjects will be permitted to continue use of all medications affecting pain throughout the study; however, dosages of these medications will be controlled and recorded during the study. Subjects will be permitted to reduce or maintain their dosages of medications affecting pain but will be asked not to increase their routine dosages of these medications above the baseline dosages that were established prior to lead placement. To be eligible for participation in the study, individuals will be required to have not added new medications affecting pain [REDACTED] prior to initiating the baseline diary according to subject reported medication history.

